### 6.2. Baseline

Unless otherwise specified, baseline is defined as the last available non-missing measurement taken prior to reference start date/time.

Assessments performed on the same day as the first IMP administration but without time information collected or with time information exactly equal to the time of first IMP administration and which are planned predose will be considered as predose. For parameters related to questionnaires, the baseline is the last value before or at the day of first administration of the IMP, independent of the time of administration. In case the participant never received IMP, the date/time of randomization will be used instead of first IMP administration date/time.

Adverse Events (AEs) and medications commencing on the reference start date will be considered post-baseline

Document:

Author:

Version Number:

V2.0

Version Date:

31JAN2024

Template No.: CS TP BS016 Revision 7 Reference: CS WI BS005

Effective Date: 01Nov2021

Statistical Analysis Plan

Page 26 of 78

unless otherwise indicated based on available start date/time combination or collected electronic case report form (eCRF) information that identifies the individual event/medication as starting prior to first IMP administration.

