BL=baseline; C3=Complement component 3; C4=Complement component 4; CH50=Total hemolytic complement; clinESSDAI=clinical ESSDAI; D=day; d/c=discontinuation; ECG=electrocardiogram; EDV=early discontinuation visit; ESSDAI=EULAR Sjögren's syndrome disease activity index; ESSPRI=EULAR Sjögren's Syndrome Patient Reported Index; EULAR=European Alliance of Associations for Rheumatology; ICF=informed consent form; IgG=immunoglobulin G; IMP=investigational medicinal product; IV=intravenous; NA=not applicable; OSS=ocular staining score; PCR=polymerase chain reaction; PD=pharmacodynamics; PK=pharmacokinetics;

A=Sjögren's syndrome-related antigen A; SS-B=Sjögren's syndrome-related antigen B; SWSF=stimulated whole salivary flow; UWSF=unstimulated whole salivary flow; W=week

argenx

; SCR=screening; SFV=safety follow-up visit;

; SGUS=salivary gland ultrasonography; SS-

<sup>a For participants who discontinue IMP but remain in the study attending on-site visits, safety follow-up assessments will occur on the previously scheduled visit closest to 56 days (±3 days) from the final IMP dose.

<sup>b The IMP discontinuation visit will be performed at the next scheduled visit after permanent IMP discontinuation and applies for participants who discontinue IMP but remain in the study. Participants who permanently discontinue IMP will perform the IMP discontinuation visit and then be asked to proceed with their regularly scheduled visits (Section 7.1.1).

<sup>c The EDV applies for participants who discontinue the study.

- d Visits 4, 6-8, 10-12, 14-16, 18-20, and 22-24 may be performed in the participant's home by a home nurse.
- e Safety, efficacy, and predose sampling activities will be performed before administering IMP.
- f Medical/surgical history includes all significant findings, surgeries, and preexisting conditions (including allergies, if any) present at screening including start and end date, if known.
- g Demographic characteristics comprise age, birth year, sex, race, and ethnicity (per local regulations). Race and ethnicity data will be source verified only if permitted by local laws.
- h Physical examination will include height and weight. Height will be measured at the baseline visit only.
-  The brief physical examination is symptom driven and will be performed as necessary to assess the ESSDAI. It will also include weight.

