- j Vital signs (Section 8.3.2) will all be measured before collecting any blood sample or administering IMP infusions.

Participants at sites performing parotid biopsy may be enrolled based on a historical biopsy obtained in the 12 months prior to baseline visit. Historical biopsy may only be used for participant enrollment when participant has not received immunomodulatory treatment for pSS (such as steroids, immunosuppressants, antimalarials, or biologics) from 6 months prior to biopsy through to screening.

-  Participant should have a biopsy at EDV only when this visit occurs after week 16.
- m Pregnancy testing will use a highly sensitive serum test at screening, and a urine test at all subsequent visits before IMP administration. Local regulations will be followed if they require more stringent or frequent testing.
- n COVID-19 testing will occur within 72 hours of baseline. Participants will be tested for SARS-CoV-2 if they are symptomatic or if applicable law requires testing. COVID-19 testing may be performed at a central or local laboratory.
- o On IMP administration visits, blood samples must be collected predose (preferably within 2 hours before the infusion). On other visits, the blood sample may be collected any time during the visit.
- p Blood samples will be collected for
- On IMP administration visits, blood samples for PK analyses will be collected predose (preferably within 2 hours before IMP administration) and postdose (within 30 minutes after the end of infusion). On other visits, a single blood sample may be collected any time during the visit. Blood samples for participants remaining in the study following IMP discontinuation will be collected for PK analysis for up to 3 weeks post IMP discontinuation.
- t ESSDAI-related laboratory tests include gammaglobulins, cryoglobulins, C3, C4 and CH50. The biological domain will be blinded postbaseline and sites will score only the clinical domains of the ESSDAI.
- u Patient-reported outcome questionnaires will be administered before any other study visit procedure where safe, and before discussions with staff about disease/treatment.
- v The IMP will be administered as an approximately 1-hour IV infusion. Participants will be monitored for safety for ≥ 30 minutes after the end of IMP administration.

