# 8.2. Efficacy Assessments

Time points for all efficacy assessments are provided in the SoA (Section 1.3).

Patient-reported outcome questionnaires are recommended to be administered before any other study assessment and may be completed  $\leq 1$  day before the visit. It is preferrable that the same physician assesses the clinical efficacy parameters at all visits.

Instructions on administering these assessments are provided in the Investigator Site File.

[figure not shown]

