# 9.3. Statistical Analyses

### 9.3.1. General Considerations

In general, data collected will be listed together with appropriate derived variables. Descriptive statistical methods will be used to analyze safety and efficacy data. Where appropriate, this may include summaries and graphical displays by time point.

Summaries will be provided by treatment assignment and overall. Summaries will include the number of observations (n), mean, SE, 95% CI, median, quartiles, minimum, and maximum for continuous measures and categorical measures sample size, frequencies, and percentages. P-values for comparing treatment groups may be provided, but these should be interpreted as supportive summary statistics.

The baseline value will be the last assessment before the first IMP administration.

All study visits will be recalculated based on actual dates. The rules for calculating the analysis visits will be documented in the SAP. Rules for imputing partial dates or missing dates will be provided in the SAP.

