#### **Table D: Efficacy Analysis Visit Definition**

For efficacy assessments, wider window will be considered as follows

Target Day	Assigned Study Day (Inclusive)		Week Assigned
	From	То	
1		1ª	Baseline
113	85	141	Week 16
169	142	176	Week 24
EDV	Final Dose - 9 days	Final Dose + 9 days	Final Dose +/- 9 days

\*Subject who permanently discontinue the treatment, assessment will be collected at IMP discontinued visit which will be performed at next scheduled visit after discontinuation. EDV: EDV visits will be performed within 7 days post final dose for those subjects who discontinue study permanently.

Questionnaires given on the day of the first administration of IMP (pre-administration or post-administration) are allocated to baseline.

Per parameter and analysis window, the non-missing value closest to the target day will be used in the analysis. If more than one non-missing value is located at the same distance from the target day, then the one latest in time will be selected for analysis. The value latest in time will be identified using, in order of preference, the assessment time, and the visit label.

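### The SAP's questionnaire baseline rule lets an ESSPRI score recorded after the first infusion replace a valid predose score, contrary to the protocol; probably few participants are affected, in an unknown direction

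*SAP*

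**What the plan says.** SAP 6.2 starts from a strict default: "baseline is defined as the last available non-missing measurement taken prior to reference start date/time". It then exempts questionnaires, for which "the baseline is the last value before or at the day of first administration of the IMP, independent of the time of administration". SAP 6.3, in the text under Table D, repeats the exemption: "Questionnaires given on the day of the first administration of IMP (pre-administration or post-administration) are allocated to baseline". The same text picks, within a window, the value nearest the target day (day 1 for baseline). If several are equally near, "then the one latest in time will be selected for analysis".

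Protocol 9.3.1 has one rule and no exemption: "The baseline value will be the last assessment before the first IMP administration". The footnotes to the Schedule of Activities (protocol 1.3) set the order of procedures: "Safety, efficacy, and predose sampling activities will be performed before administering IMP", and "Patient-reported outcome questionnaires will be administered before any other study visit procedure where safe". Protocol 8.2 is softer on questionnaires, recommending rather than requiring that they come first, and it accepts completion up to one day before the visit.

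**The concern.** ESSPRI is a questionnaire, so the exemption applies to it. It is one of the five CRESS items. It carries 3 STAR points, where 5 are needed for response. It also has its own secondary endpoints, a responder proportion and a change score (SAP 2, Table A).

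A score given after the infusion is no longer a pre-treatment measurement. Protocol 2.3.1 says infusion-related reactions can arise during an infusion or in the following 48 hours, so a post-infusion entry could come after one. The scheduled week 24 score has no same-day infusion behind it, because the last dose is at week 23 (protocol 4.1). The two ends of the change score could then be taken under different conditions. At stake is whether some participants' responder status depends on which of two day 1 entries the program selects.

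**Working it through.** The plan gives no figure for this point. Its one design figure, a lower one-sided 95% Wilson limit of about 33% at 10/20 responders (protocol 9.5, SAP 3.2), reproduces as 32.7% and does not depend on the baseline rule.

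**Which value each rule selects**

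| ESSPRI entries | Protocol 9.3.1 | SAP 6.2 and 6.3 |
|---|---|---|
| One predose entry | predose | predose |
| Day −1 entry, then post-infusion day 1 entry | day −1 | post-infusion (later, and nearer day 1) |
| Predose day 1 entry, then post-infusion day 1 entry | predose | post-infusion (equally near, later kept) |
| Post-infusion day 1 entry only | no baseline | post-infusion |

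The rules differ only when there is a post-infusion day 1 entry.

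**Effect on the ESSPRI item**

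ESSPRI is the mean of three 0–10 items. Response is a fall of at least 1 point or at least 15% from baseline (SAP 14.1.1). For baseline B, the highest week 24 score that counts is therefore max(B − 1, 0.85B). The scores below are assumed, because the documents give none.

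- *Post-infusion score higher.* Predose 6.0; one more point on each item gives 7.0. At week 24 the score is 6.0. From 6.0 the fall is 0, no response. From 7.0 the fall is 1.0, a response through the 1-point criterion (as a percentage it is 1.0/7.0 = 14.3%, below 15%).
- *A smaller rise.* Predose 6.0; one item up by one point gives 6.33. At week 24 the score is 5.33. From 6.0 the fall is 0.67, or 11%, no response. From 6.33 it is 1.0, a response.
- *Post-infusion score lower.* Predose 6.0, post-infusion 5.33. The limits are max(5.0, 5.10) = 5.10 under the protocol and max(4.33, 4.53) = 4.53 under the SAP. A week 24 score of 5.0 or 4.67 is a response under the protocol only.

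The 15% must be taken of the baseline actually used. Taking it of the predose score (15% of 6.0 = 0.9) would suggest that a rise of 0.9 creates a response. It does not: from 6.9 back to 6.0 is 0.9/6.9 = 13.0%, which meets neither criterion.

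**Effect on the composites**

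- CRESS needs at least 3 of 5 items, so a changed ESSPRI item changes CRESS only when exactly 2 of the other 4 are met.
- STAR needs 5 points and ESSPRI gives 3, so STAR changes only when the other domains total 2, 3 or 4.
- The target of about 15 + 15 = 30 participants at 2:1 gives about 20 and 10. One changed result is 1/20 = 5% or 1/10 = 10% of an arm.

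**The case against.** The strongest reply is that the situation should hardly arise. The Schedule of Activities lists ESSPRI once at baseline and not at screening, efficacy work precedes dosing, and questionnaires come first where safe. Nothing in the documents provides for a second entry. If a participant's only entry is post-infusion, the change proposed below still uses it in the main analysis. Moreover, ESSPRI asks about the previous two weeks (SAP 14.1.1), so a score given shortly after an infusion of about one hour describes almost entirely pre-treatment time. All of this stands, and it keeps the point small. It does not justify letting a later post-infusion entry override an existing predose one.

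The exemption might be defended as a way to keep day 1 questionnaires without a clock time. SAP 6.2 already covers these: day 1 assessments planned as predose and lacking a time are treated as predose.

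A reader might infer that the rule favours efgartigimod by inflating its baselines. The documents do not support that. They give no count of post-infusion entries and no difference in reactions between arms, the study is double-blinded, and the lower-score case above works against response.

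A reader might also infer an undeclared change from the protocol. The legible items of SAP 3.4 do not mention it, but part of that list is redacted, so this cannot be established. The exemption itself is stated openly in SAP 6.2 and 6.3.

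**Conclusion.** The point holds as a conflict between the SAP and the protocol. When triggered, the SAP rule assigns a post-treatment baseline to an item of the primary endpoint even though a predose value exists. It affects only participants with a post-infusion day 1 entry. They are probably few and may be none; the documents give no number. With a two-week recall the shift is likely to be small, and its direction is unknown. The ceiling per changed CRESS result is 5% of the efgartigimod arm or 10% of the placebo arm, reached only when exactly two other items are met. These percentages assume arms of about 20 and 10, and the score examples are illustrations. No design figure changes. A correction is worth making because the wording is explicit, the item feeds the primary endpoint, and the change is cheap.

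**What to change.** Amend SAP 6.2 and the text under Table D in SAP 6.3 together:

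1. Use the last questionnaire value before the start of the first infusion whenever one exists. Untimed day 1 values that were planned predose count as predose, as SAP 6.2 already provides.
2. Only if there is no such value, use the same-day post-infusion value and flag it.
3. Repeat the CRESS, STAR and ESSPRI analyses with flagged baselines set to missing, and report how many participants are flagged in each arm.
4. List any remaining departure from protocol 9.3.1 in SAP 3.4, if the redacted text does not already do so.

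The cost is about two sentences and one programming condition on the entry time, plus the sensitivity run if anyone is flagged. No participant loses a baseline in the main analysis.

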## **6.3. Windowing Conventions**

All assessments, including unscheduled assessments, will be allocated to an analysis visit window. Tables and listings will be based on analysis windows defined below. Allocations of assessments will be performed using their relative day.

Table C: Non-efficacy Analysis Visit Definition

Phase	Target Day	Assigned Study Day (Inclusive)		Week Assigned
		From	То	
		-28	-2	Screening
Treatment	1		1ª	Baseline
	8	1ª	11	Week 1
	15	12	18	Week 2
	22	19	25	Week 3
	29	26	32	Week 4
	36	33	39	Week 5
	43	40	46	Week 6
	50	47	53	Week 7
	57	54	60	Week 8
Treatment	57 + (x*7)	57 + (x*7) - 3	57 + (x*7) + 3	Week 8+x b

Document:
Author: Version Number: V2.0

Version Date: 31JAN2024

Template No.: CS\_TP\_BS016 Revision 7 Reference: CS\_WI\_BS005

Effective Date: 01Nov2021

Statistical Analysis Plan

Page 27 of 78

Safety Follow-up	Final dose + 56 days	(Final dose + 56 days ) - 3	(Final dose + 56 days) + 3 days	Week xx+ 56 days
		days		

<sup>a An assessment on day 1 before the first administration of IMP will be allocated to baseline.

Some parameters which are not collected at every visits, visit window will be combined (by extending window with previous or subsequent visits).

For e.g. Week 3 is not protocol scheduled visit for RF, IGG and Brief Physical Examination. Hence, visit window can be combined with Week 2 and Week 4. The non-missing value closest to the target day will be used in the analysis in case of multiple observations.

Table C: Non-efficacy Analysis Visit Definition (continued: )

Phase	Target Day	Assigned Study Day (Inclusive)		Week Assigned
		From	То	
		-28	-2	Screening
Treatment	1		1	Baseline
	8	1ª	11	Week 1
	15	12	22	Week 2
	29	23	43	Week 4
	57	44	71	Week 8
	85	72	99	Week 12
	113	100	127	Week 16

Document: Author:

Version Number: V2.0

31JAN2024

Version Date:

Template No.: CS TP BS016 Revision 7 Reference: CS WI BS005

Effective Date: 01Nov2021

<sup>b considers value of x, starting from 1 to up until 16 to get visit windows for Week 9 to Week 24. The above Table C contains visit window for assessments at every week. Kindly refer respective visit window table for other assessments.

Statistical Analysis Plan

Page 28 of 78

141	128	156	Week 20
169	157	184	Week 24
EDV	Final Dose - 9 days	Final Dose + 9 days	Final Dose +/- 9 days

Note: After treatment period ends, safety follow-up will be of approximately 7 weeks (56 days  $\pm$  3 days) for participants who do not roll over to the Open Label Extension (OLE) study ARGX-113-2211.

For Clinical laboratory assessments (Including Pregnancy and Urinalysis), we do not have week 2 visit, as in that case the following window.

Table C: Non-efficacy Analysis Visit Definition (continued: )

Target Day	Assigned Study Day (Inclusive)		Week Assigned
	From	То	
	-28	-2	Screening
1		1	Baseline
8	1ª	11	Week 1
29	12	43	Week 4
57	44	71	Week 8
85	72	99	Week 12
113	100	127	Week 16
141	128	156	Week 20
169	157	184	Week 24

Document:
Author: Version Number: V2.0

Version Date: 31JAN2024

Template No.: CS\_TP\_BS016 Revision 7 Reference: CS\_WI\_BS005

Effective Date: 01Nov2021

Statistical Analysis Plan

Page 29 of 78

EDV	Final Dose - 9	Final Dose + 9	Final Dose +/- 9
	days	days	days

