### 7.1. Discontinuation of IMP

### 7.1.1. Permanent Discontinuation

Permanent discontinuation of IMP occurs when the participant stops receiving the IMP before the end of the study, does not resume receiving IMP, and does not withdraw informed consent. The investigator will document the primary reason for early discontinuation of IMP. Participants who permanently discontinue IMP will complete the IMP discontinuation visit and will be encouraged to remain in the study and attend any previously scheduled visits. Blood samples for participants remaining in the study following IMP discontinuation will be collected for PK analyses as per the SoA (Section 1.3) for up to 3 weeks post IMP discontinuation.

If the participant is unable or unwilling to attend study visits for any reason, the study site will perform an EDV and the SFV. The study sites will attempt to perform the EDV within the 7 (+2) days after the participant's final IMP administration. The SFV will occur  $56 \pm 3$  days after the participant's final IMP administration.

Additionally, the following circumstances will result in the permanent discontinuation of IMP:

- The participant becomes pregnant or intends to become pregnant (refer to Section 8.3.5).
- The investigator considers discontinuing IMP is in the participant's best interest (the sponsor will be informed).
- The participant develops an SAE or AE that contraindicates further administration of IMP in the investigator's opinion or an AE of CTCAE severity grade 4 that is considered related to IMP by the sponsor.
- The participant receives a prohibited medication or substance (refer to Section 6.9).

Participants permanently discontinuing IMP will be ineligible for roll over to the OLE study.

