## 8.3.5. Pregnancy Testing

WOCBP will be tested for pregnancy by serum at screening. Urine tests for pregnancy will occur at the time points specified in the SoA (Section 1.3).

Pregnancy testing in WOCBP will be conducted at the end of relevant systemic exposure (ie, at the SFV).

Additional pregnancy testing may be performed as necessary by the investigator or required by local regulations, to establish the absence of pregnancy at any time during the study.

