The following summaries will be provided for laboratory data:

- Continuous laboratory parameters to be summarized using descriptive statistics of actual values and changes from baseline at each analysis visit.
- Laboratory toxicity grades to be presented as cross-tabulations of the toxicity at each postbaseline analysis visit
  and at the worst-case analysis visit versus the baseline toxicity.
- Laboratory abnormalities as cross-tabulations of the abnormality at each postbaseline analysis visit and at the
  worst-case analysis visit versus the baseline abnormality. The number of participants with treatment-emergent
  abnormalities will also be shown. The denominator for the percentage is the total number of participants per
  treatment arm and per analysis visit in the SAF.
- Listing of participants with any post-baseline abnormality or toxicity grade ≥1.

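### SAP 6.3: the laboratory and RF/IgG window tables have no safety follow-up row, and the EDV window starts before the final dose, so follow-up results are left unassigned or labelled as treatment weeks

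*SAP*

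**What the plan says.** SAP 6.3 opens with a general rule: "All assessments, including unscheduled assessments, will be allocated to an analysis visit window". Allocation is by relative day, and tables and listings are built on the resulting windows.

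The weekly Table C includes a Safety Follow-up row whose upper limit is "Final dose + 56 days) + 3 days", with a matching lower limit 3 days before the target. Its footnote restricts its use: "The above Table C contains visit window for assessments at every week. Kindly refer respective visit window table for other assessments".

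Two continued tables follow. One covers RF, IgG and the brief physical examination. The other is introduced by "For Clinical laboratory assessments (Including Pregnancy and Urinalysis), we do not have week 2 visit, as in that case the following window". Both end with Week 24 (days 157-184) and an EDV row from 9 days before to 9 days after the final dose. Neither has a Safety Follow-up row. Table D (efficacy) has the same EDV row. In all three the target-day cell reads only EDV, with no number.

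The protocol's schedule of activities marks hematology/chemistry, urinalysis, pregnancy testing and total IgG at the SFV. On EDV timing, protocol 7.1.1 says: "The study sites will attempt to perform the EDV within the 7 (+2) days after the participant's final IMP administration". The Table D footnote likewise places the EDV after the final dose, and only for participants who leave the study.

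The laboratory output depends on these windows: "Continuous laboratory parameters to be summarized using descriptive statistics of actual values and changes from baseline at each analysis visit". SAP 15 summarises PD by analysis visit in the same way.

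**The concern.** A sample that matches no window has no column in a by-visit table. One that matches the wrong window appears under a label that misdescribes it. Both can happen here.

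The protocol gives reduced IgG as the reason infections are events of special interest, so readers will want to see whether IgG and the laboratory values recover off drug. For participants who complete treatment and do not enter the extension, week 24 is only 7 days after the week 23 dose. The SFV is their only later scheduled sample. If it has no window, the by-visit summaries show no recovery. If an early leaver's SFV is labelled as a treatment week, values taken about 8 weeks off drug are averaged with values from participants still being dosed.

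The EDV row raises a second problem. Its lower half lies before the final dose, where no EDV can occur, and on-treatment samples fall there.

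**Working it through.** **Inputs.** First dose is day 1 (SAP 6.1). The final scheduled dose is at week 23 (protocol 4.1; SAP 3.1). The SFV is final dose + 53 to + 59 days (weekly Table C; protocol 7.1.1). From day 44 both continued tables have the same unbroken windows: Week 8 (44-71), Week 12 (72-99), Week 16 (100-127), Week 20 (128-156), Week 24 (157-184). EDV is final dose - 9 to + 9.

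**Reproducing the plan's figure.** Week k falls on day 1 + 7k, so Week 24 = 1 + 168 = 169. The SAP's own rule gives 57 + 7 × 16 = 169. The week 23 dose is on day 1 + 161 = 162.

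**Where the SFV lands.** For a final dose at week k, the SFV runs from day (1 + 7k) + 53 = 54 + 7k to day (1 + 7k) + 59 = 60 + 7k. It is never within 9 days of the final dose, so the EDV row cannot catch it.

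| Final dose | Condition | SFV label |
|---|---|---|
| Weeks 0-17 | 60 + 7k ≤ 184 | a treatment week, Week 8 to Week 24 |
| Week 18 | days 180-186 | Week 24 up to day 184, then none |
| Weeks 19-23 | 54 + 7k > 184 | none |

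- Full course (k = 23): days 215-221. That is 31 to 37 days after the last week window closes on day 184, and outside EDV (162 ± 9 = 153-171).
- Final dose at week 8 (day 57): days 110-116. An SFV exactly on time is day 57 + 56 = 113, which is the Week 16 target day.

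For weeks 0-17 the mislabelling concerns participants who have left the study. Those who stop IMP but stay have their safety follow-up assessments at the nearest scheduled visit (schedule of activities, footnote a), so a week label is correct for them.

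**What the EDV row admits.** An on-schedule sample at week x, at or before a final dose at week k, falls inside when 0 ≤ 7(k - x) ≤ 9, that is, k = x or k = x + 1.

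- Hematology/chemistry, on-treatment weeks 4, 8, 12, 16, 20: final doses at weeks 4, 5, 8, 9, 12, 13, 16, 17, 20, 21, or 10 of 24 possible weeks.
- Total IgG, with weeks 1 and 2 added: also weeks 1, 2 and 3, or 13 of 24.
- Table D, on-treatment efficacy visit at week 16: final doses at weeks 16 and 17.

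**Which sample would be chosen.** With a final dose on day 57 the EDV window is days 48-66. The week 8 pre-dose sample is on day 57; an EDV 7 days after the dose is on day 64. If the target is the final dose, the distances are 0 and 7 days and the on-treatment sample wins. If the target is final dose + 7, they are 7 and 0 and the EDV sample wins. The SAP does not say which applies.

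**Overlap.** For a final dose at week 23 the EDV window (153-171) overlaps Week 20 on days 153-156 and Week 24 on days 157-171. No rule says which label prevails.

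**The case against.** The strongest reply is that the SAP plainly means to include these data. A note after the RF/IgG table restates follow-up as 56 ± 3 days. SAP 18.2.1 considers laboratory data up to 60 days after IMP discontinuation. SAP 15 refers to planned time points, of which the SFV is one for IgG. The continued tables were introduced to merge weeks without sampling, which is no reason to drop the follow-up row. The intent stands, but none of these statements assigns a window, and the weekly table's footnote sends these assessments elsewhere.

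Three stronger readings are tempting, and the documents do not support them.

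- That all SFV results drop out. They are wholly unassigned only for final doses at weeks 19-23, and even then they remain in the listings. SAP 6.4 uses every post-baseline value for the worst-case laboratory visit.
- That EDV summaries will show on-treatment samples. This follows only if the final dose is taken as the target. If the EDV itself is the target, the closest-value rule picks the true EDV sample when one exists.
- That a completer's week 24 sample becomes an EDV result. It meets the numeric limits, but the schedule of activities and the Table D footnote reserve the EDV for study discontinuers. The fault is that the window rows do not repeat that restriction.

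It is also fair that categorical laboratory results such as pregnancy tests are only listed, so they lose no by-visit summary. The retained outputs do not fully substitute for IgG, however: the extra PD points in SAP 15 are the maximum drop and the minimum value, which show the nadir and not recovery.

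**Conclusion.** The point holds as a defect in SAP 6.3. Read literally, the window rules give SFV laboratory and IgG results no analysis visit for final doses at weeks 19-23, split them at week 18, and put study discontinuers' results under a treatment week for weeks 0-17. The EDV limits contradict the protocol and the SAP's own footnote, and they make selection of an on-treatment sample possible but not certain.

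The size is modest. About 30 participants are planned, those entering the extension have no SFV, and the documents do not say how many will not roll over. The affected outputs are descriptive safety and PD summaries. The primary result is not at risk from the missing row: the clinical components of CRESS are not assessed at the SFV, and the main estimand scores early treatment stoppers as non-responders.

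The arithmetic assumes dosing on schedule and windows applied by study day alone. SFV sampling is confirmed for total IgG and the safety laboratory tests; it cannot be confirmed for RF from the legible schedule.

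**What to change.** 1. Carry the existing Safety Follow-up row (final dose + 56 ± 3 days) into both continued tables.
2. In both continued tables and Table D, limit the EDV window to after the final dose through + 9 days, give it a numeric target of final dose + 7, and apply it only to participants with a recorded EDV.
3. Add a precedence rule: for participants who have left the study, recorded EDV and SFV samples go to those visits and not to an overlapping week window. This is needed because the new SFV row overlaps week windows for final doses up to week 18, and an EDV up to day 171 still overlaps Week 24.

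For Table D the SAP should say explicitly how step 3 applies. An EDV 7 days after a final dose at weeks 20-23 falls on day 148, 155, 162 or 169, inside the Week 24 efficacy window (142-176). Relabelling it would change which results enter the secondary analyses, which SAP 14.2 bases on observed data.

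The cost is SAP wording, a small programming change and one extra column in by-visit tables. No new data, visits or samples are needed.
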